4.2.6 Product Administration

Before Ordering Study Product: Pregnancy prevention counseling must be conducted, and pregnancy test results must be confirmed negative for females of childbearing potential. Subjects must be clinically evaluated with a medical history review and injection site assessment. Blood samples must be collected after randomization but prior to product administration per Appendix III.

Ordering Study Products: The site must follow standard operating procedures to order study product from the Pharmacy.

Product Administration Procedures: It is recommended, but not required, that the first vaccination be administered into the non-dominant arm. It is preferred, but not required, to alternate arms for a subsequent product administration, if applicable. When choosing an arm for the product administration, clinicians should consider whether there is an arm injury, local skin problem or significant tattoo that precludes the administration of the study product or will interfere with evaluating the arm after product administration. All product administrations will be administered IM into upper arm deltoid muscle by needle and syringe.

For groups receiving adjuvant, the adjuvant will be added by the site pharmacist prior to delivery to the clinic for administration.

Prior to each product administration, the syringe MUST be inverted 5 times. “*Inversion*” of a prepared syringe is defined as a gentle, complete 180 degree rotation, do not “*shake*” the syringe.

For the Second Product Administration: If a subject presents with fever or other signs of significant illness on the day of the product administration visit, do not order or administer study product. Unscheduled visits may be used to evaluate the subject’s condition and the administration visit should be rescheduled within the allowable visit window.

If a subject is undergoing evaluation and/or treatment for a medical condition at the time of the second scheduled administration visit, then vaccinations should be delayed until the condition has resolved or is considered stable. Contact the IND Sponsor for questions about resuming or discontinuing vaccinations as needed.

To schedule a product administration visit outside of the allowable visit window, the site must document PI approval.

Post Product Administration Procedures: Following product administration, all subjects will be observed for a minimum of 30 minutes. Vital signs (temperature, blood pressure, pulse, and respiratory rate) will be collected at least 30 minutes after product administration, prior to subject departure from the clinic. The injection site will be inspected for evidence of local reaction.

In keeping with good medical practice, acute medical care will be provided to subjects for any immediate allergic reactions or other injury resulting from participation in this research study.

4.2.7 Safety Evaluations and Follow-up after Product Administration

Prior to the end of the visit after each product administration, subjects will be given a “Diary Card” to use as a memory aid, on which to record temperature and symptoms daily for 7 days. Subjects will also record the day’s highest measured temperature and measurement of the largest diameter of redness and swelling at injection site.

Subjects will be trained and encouraged to use a secure electronic database but have the option to complete a paper diary card. When the parameters are recorded directly by the subject electronically, the subject’s electronic record will be the source for these data. The paper diary card may be used as a source document. When neither a paper nor electronic diary card is available, the study clinician will note the source of reactogenicity information recorded in the study database.

The solicited signs and symptoms on the diary card will include the following parameters: pain/tenderness at injection site, erythema (redness) at injection site, induration (swelling) at injection site, temperature, unusually tired/feeling unwell, muscles aches (other than at injection site), arthralgia (joint pain), headache, chills and nausea.

Follow-up on subject well-being will be performed by telephone 2 days post each product administration. Subject diaries are reviewed for accuracy and completeness at follow-up in-person visits. Clinicians will follow and collect resolution information for any reactogenicity symptoms that are not resolved within 7 days.

Events following any study product administration that may require clinical evaluation include rash, urticaria, arthralgia, fever of 38.5°C (Grade 2) or higher lasting greater than 24 hours, or significant impairment in the activities of daily living. Additionally, other clinical concerns may prompt a study visit based on the judgment of a study clinician. If a skin lesion or other unexpected reaction at the injection site occurs in this study, we may ask the subject to allow us to take a photograph. If the subject agrees, he/she will be asked to sign a site-specific photography informed consent form.

Any subject who receives at least one vaccination is expected to continue with safety follow-up through study Week 36.

4.2.8 Blood Sample Collection

At intervals throughout the study, blood will be drawn for safety evaluations and immunologic assays. Blood will be drawn from the arm veins of subjects by standard phlebotomy procedures. As per NIH Clinical Center (CC) guidelines, total blood volume drawn from adult subjects (who weigh at least 50 kg) will not exceed 550 mL in any 8-week period. The site must also follow institutional policy for blood collection.

4.2.9 Concomitant Medications

Only routine prescription medications at the time of randomization are recorded in the study database. Subsequently, concomitant medications are only updated or recorded in the database if there is an occurrence of an AE that requires expedited reporting or if the subject develops a new

chronic condition that requires ongoing medical management. Receipt of a FDA-approved vaccine at any time during the study will be recorded in the database (clinicians should work with subjects regarding the timing of licensed vaccines relative to product administration). Otherwise, the concomitant medication changes throughout the study will be recorded in the subject's chart as needed for general medical records, but will not be recorded in the database.

4.3 Dose Escalation

There will be two dose escalation reviews in this study. The Protocol Safety Review Team (PSRT, Section 8.8.1) will conduct an interim safety review of all available data at the time of the review. The PSRT must assess the data as showing no significant safety concerns before escalation to the next dose.

Randomization will begin in Group 1 (6 mcg WEVEE) and Group 2 (6 mcg WEVEE + alum). No more than one subject will be randomized and vaccinated per day for the first 3 subjects at each dose.

- 1) The first interim safety review for dose escalation will be conducted when safety data for the first 3 subjects to receive 6 mcg WEVEE become available for the visit two weeks after vaccination (Visit 03 /Day 14). Subject randomizations and vaccinations in Group 1 and Group 2 may continue during the interim safety review; however, randomizations should be completed prior to beginning Group 3 and 4 randomizations.

If the 6 mcg dose of WEVEE is assessed as not showing safety concerns by the PSRT, randomization can begin for Group 3 and Group 4.

Randomization will proceed in Group 3 (30 mcg WEVEE) and Group 4 (30 mcg WEVEE + alum).

- 2) The second interim safety review for dose escalation will be conducted when safety data for the first 3 subjects to receive 30 mcg WEVEE become available for the visit two weeks after vaccination (Visit 03 /Day 14). Subject randomizations and vaccinations in Group 3 and Group 4 may continue during the interim safety review; however, randomizations should be completed prior to beginning Group 5 and 6 randomizations.

If the 30 mcg dose is assessed as safe, randomization can begin for Group 5 (60 mcg WEVEE) and Group 6 (60 mcg WEVEE + alum).

If an initial study vaccination is not completed or there are discontinuations from the study before there are sufficient data to conduct the dose escalation review, then extra subjects may be randomized at the same dose level in order to have the requisite data on at least 3 subjects in these groups. The IRB will be provided with documentation of the safety review process and notification of the dose escalation. Consultation with the IRB and FDA, if needed, as per study pause criteria ([Section 4.4](#)) will occur if indicated by the review. One outcome of a dose escalation review may be to recommend evaluation of additional subjects at the current dose level and reassess for safety before proceeding to a higher dose level.

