4.4 Pausing and Resuming the Study

4.4.1 Criteria for Pausing the Study

The Protocol Chairs, in consultation with site PI, will closely monitor and analyze study data as they become available and will make determinations regarding the presence and severity of AEs. The administration of study products and new enrollments will be paused and the IND Sponsor will be promptly notified according to the following criteria:

- **One** (or more) subject experiences a **SAE** assessed as related to the study product (with or without adjuvant).
- **Two** (or more) subjects experience the same **Grade 3 or higher AE** assessed as related to the study product (with or without adjuvant). Pause is not required for self-limited solicited reactogenicity (generally defined as resolved within 2 days of onset) following any study vaccination.
- **Three** (or more) subjects experience the same or similar **Grade 3 solicited AE** (other than injection site redness or swelling) lasting ≥ 24 hours.

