4.4.3 Dose-Limiting Toxicity

Dose-limiting toxicity is defined in this protocol as an AE that prevents a dose escalation of the study vaccine or prevents continuation of product administrations at a given dose level. If the study is paused as per criteria in [Section 4.4.1](#) and a decision is made to not resume the study vaccinations at the current dose, then the safety review will include a decision as to whether or not to continue accrual at a lower vaccine dose that was evaluated to be safe in order to achieve the target study accrual of 30 subjects.

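### Section 4.3 spaces the first three subjects at each dose by a day but requires no contact with one before the next is vaccinated

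*Combined protocol and SAP*

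**What the plan says.** Section 4.3 sets the pace within a dose level in one sentence: "No more than one subject will be randomized and vaccinated per day for the first 3 subjects at each dose". It names nothing that must be known about one of these subjects before the next is dosed, and it sets no daily limit from the fourth subject on. The condition it does set lies between dose levels: "The PSRT must assess the data as showing no significant safety concerns before escalation to the next dose". That review uses Day 14 data on the first three subjects, and dosing at the current level may go on while it is held.

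Contact after an injection is set elsewhere:

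- Section 4.2.6: "Following product administration, all subjects will be observed for a minimum of 30 minutes".
- Section 4.2.7: "Follow-up on subject well-being will be performed by telephone 2 days post each product administration". Appendix III gives this call (Visit 02A) a window of +1 day and lists nothing on Day 1.
- Section 4.2.7, on the 7-day diary: "Subjects will be trained and encouraged to use a secure electronic database but have the option to complete a paper diary card". Staff review of the diary is placed at in-person visits, the first of which is Day 14.

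Several controls also operate within a dose level. Section 8.8.1 gives the site PI daily review and the Protocol Safety Review Team (PSRT) weekly review. Under Section 4.4.1 the Protocol Chairs, with the site PI, "will closely monitor and analyze study data as they become available". Dosing pauses after one related SAE, after the same related Grade 3 or higher event in two subjects, or after a similar Grade 3 solicited event lasting at least 24 hours in three. The two-subject rule carries an exception: "Pause is not required for self-limited solicited reactogenicity (generally defined as resolved within 2 days of onset) following any study vaccination". Section 4.4.3 counts as dose-limiting an event that blocks escalation or "prevents continuation of product administrations at a given dose level".

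Letters of Amendment #1 and #3 do not touch Section 4.3. Letter #2 and the consent form were not in the text reviewed.

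**The concern.** A stagger protects the next subject only if something is learned about the previous one in the interval. Here the interval is fixed in calendar days, and the contact that would use it is scheduled later. A reaction that starts after the observation period reaches the site before the call only if the subject reports it or staff open an electronic diary entry. A paper entry stays with the subject.

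Section 1.4 confirms that the product has not been given to humans before. The Day 14 reviews protect subjects at the next dose level. They do not protect the second and third subjects at the same level, or the other 7 of the 10 planned there (two groups of 5, less 3). After 60 mcg there is no further escalation review.

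**Working it through.** The plan states no figure to reproduce here; the check is a calendar.

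**Inputs.** The minimum gap between the first three subjects is g = 1 day (4.3). A subject dosed on day d is called on day d + 2, or d + 3 if the window is used (4.2.7, Appendix III). The next subject is dosed on day d + g. The fourth subject is placed at the same gap for illustration.

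**Fastest permitted pace, g = 1.**

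| Subject | Dosed | Call due | Next subject dosed |
|---|---|---|---|
| 1 | Day 0 | Day 2 or 3 | Day 1 |
| 2 | Day 1 | Day 3 or 4 | Day 2 |
| 3 | Day 2 | Day 4 or 5 | Day 3 |

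In each row the next injection comes before the preceding subject's call, by (d + 2) − (d + 1) = 1 day for a call on time and (d + 3) − (d + 1) = 2 days for a late one. The same holds at each of the three doses, because the rule is the same.

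**Slower paces.** The call falls on an earlier day than the next injection only if g > 2 (on time) or g > 3 (late).

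| Gap g | Call on time (d + 2) | Late call (d + 3) |
|---|---|---|
| 1 day | after the next injection | after |
| 2 days | same day, order not fixed | after |
| 3 days | before | same day, order not fixed |
| 4 days | before | before |

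Spacing alone would therefore need 4 days to guarantee that the call comes first. A required contact does this at any pace. With a check on day d + 1 before the next randomization, dosing on Days 0, 1, 2 and 3 remains possible.

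**Do the other controls fill the gap?** Each was read for whether it obtains information or acts on it.

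- Daily PI review, the Chairs' monitoring and weekly PSRT review work on data in hand. None requires a contact on Day 1.
- The diary can inform the site early, but only through an electronic entry that someone views. Its solicited items do not include rash, urticaria or breathing difficulty, although Section 4.2.7 names rash and urticaria as events that may need clinical evaluation.
- Only the related-SAE rule can pause dosing after one subject. At 6 mcg, where no earlier subjects exist, the two-subject rule cannot be met until two have been dosed, nor the three-subject rule until all three have.

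**The case against.** The strongest reply is that this is a matter of proportion. VLPs cannot replicate (1.2). The product is made by the same methods as the chikungunya VLP vaccine, which had no SAEs in Phase 1 and no related SAEs in Phase 2, where 201 subjects were in the vaccine group (1.4.1). The starting dose of 6 mcg is below the 10–40 mcg range studied with that vaccine (8.5.1), and licensed VLP vaccines use 10–60 mcg per injection (1.5). One site enrols (9.6), so a reported reaction reaches the team that randomizes the next subject. A single related SAE, which under Section 5.2 may be an important medical event without hospitalization, stops dosing. The PI and Chairs may also act on less. Nothing in the documents shows a delayed severe reaction that a next-day call would have caught.

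All of this stands. It lowers the risk and rules out calling the design unsafe. It does not answer the narrower point, because every one of these controls begins once the site knows something.

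A second reply concerns time. The one-per-day rule already puts a night between injections. If dosing falls between 08:00 and 17:00 (an assumption), the gap at one-day pace is 24 + 8 − 17 = 15 to 24 + 17 − 8 = 33 hours. A reader might infer that the fix lengthens follow-up from 30 minutes to that range. It does not: the hours elapse already, and what is added is a contact within them.

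**Conclusion.** The point holds as a worthwhile, inexpensive safety improvement. At the fastest permitted pace, the preceding subject's scheduled call falls 1 to 2 days after the next injection at every step, and no other scheduled step obtains information on that subject after the 30-minute observation. This rests on the one-day pace, which is permitted but not necessarily expected, and on the unseen Letter of Amendment #2 not having changed Section 4.3.

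Four stronger readings are not supported:

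- **That the plan contradicts itself.** It does not; a step is absent.
- **That the site would know nothing.** A subject may telephone or make an electronic entry that is viewed, and the reviews and pause rules would then operate.
- **That all three subjects must be dosed before any call.** They can be. However, the third injection and the first subject's on-time call both fall on Day 2, so that call may come first.
- **That the fix would bring the scheduled calls ahead of the injections.** Visit 02A stays at Day 2, so at one-day pace the scheduled call still follows the next injection. The gain is a required next-day contact where none exists now, and should not be scored as an improvement in the timing of the scheduled call.

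**What to change.** Add to Section 4.3, for the first three subjects at each dose:

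1. Site staff make and record direct contact with the preceding subject, by call or visit. Viewing the diary alone does not count. The contact takes place no earlier than the calendar day after dosing and before the next subject is randomized. It asks about any symptoms, including rash, urticaria and breathing difficulty.
2. A contact is on record for all three before the fourth subject is randomized.
3. If the subject cannot be reached, the next randomization waits.
4. If the contact finds an SAE, or a Grade 3 or higher event not judged unrelated to study product, the site PI and Protocol Chairs record a decision to proceed or hold before the next injection. Solicited reactogenicity already resolved at the contact is exempt; a Grade 3 symptom still present is not.
5. This step is additional to the Section 4.4.1 pause criteria, which are unchanged.

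The check belongs before randomization because Section 4.2.4 requires randomization and dosing on the same day. The wording on relatedness in item 4 also covers solicited events, which Section 5.1 records without attribution.

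**Cost.** A few sentences and up to 3 × 3 = 9 brief contacts by existing staff. There may be an occasional delay of about a day when a subject cannot be reached or an event is under review. Doses, Visit 02A and the one-per-day rule stay as they are.

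**Limit.** A reaction that starts after the next-day contact may still be unseen until the Day 2 call.

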6.5 Randomization of Intervention Assignments

Randomizations will be done online using an electronic randomization system. The randomization code will be prepared by the Protocol Statistician and included in the randomization module for the trial. The randomization code will link to the intervention assignment. The electronic data system will assign each subject a randomization code after eligibility has been confirmed in the system.

At the beginning of the study, subjects will be randomized 1:1 to Groups 1 and 2. If the criteria for the first dose escalation are met and procedures for the interim safety review are completed, subjects can be randomized 1:1 to Groups 3 and 4. For practical purposes, accrual and randomization to Groups 1 and 2 should be completed as per study plan before accrual to Groups 3 and 4 begins.

If the criteria for the second dose escalation are met and procedures for the interim safety review are completed, subjects can be randomized 1:1 to Groups 5 and 6. For practical purposes, accrual and randomization to Groups 3 and 4 will be completed as per study plan before accrual to Groups 5 and 6 begins.

The subject and study clinicians will be informed on the subject's group assignment upon completing randomization in the electronic data collection system.

To decrease the potential for subject dropouts during the period between randomization and product administration will occur on Day 0 when eligibility is confirmed. If subjects accrued to a study group do not complete the number of vaccinations and follow-up duration specified, then additional subjects may be accrued in that group.

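### Section 4.3 can open the next alum group with fewer than 3 alum recipients followed to Day 14, because the escalation trigger counts subjects by dose and not by formulation

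*Combined protocol and SAP*

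**What the plan says.** Section 4.3 provides for two escalation reviews. The first is held "when safety data for the first 3 subjects to receive 6 mcg WEVEE become available" for the Day 14 visit (Visit 03); the second uses the same rule at 30 mcg. Neither trigger says how many of the three must have received alum. After a favourable first review, "randomization can begin for Group 3 and Group 4", so both formulations at the next dose open on one decision. Groups 5 and 6 open the same way after the second.

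Dosing need not wait for the review: "Subject randomizations and vaccinations in Group 1 and Group 2 may continue during the interim safety review". If subjects drop out before a review, extra subjects may be randomised "in order to have the requisite data on at least 3 subjects in these groups", which does not say three per group. The review team (PSRT) also has discretion: "One outcome of a dose escalation review may be to recommend evaluation of additional subjects at the current dose level".

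Section 6.5 refers back to these criteria and adds none for alum. It fixes the allocation ("At the beginning of the study, subjects will be randomized 1:1 to Groups 1 and 2") and the order of accrual ("For practical purposes, accrual and randomization to Groups 1 and 2 should be completed as per study plan"). Completing randomisation means that all subjects at the dose have been vaccinated, since section 4.2.4 puts both on one day. It does not mean that they have reached Day 14.

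**The concern.** Section 3.1 makes safety with adjuvant a primary objective in its own right. Section 1.4 reports no human experience with the vaccine, so the vaccine-alum combination is also being given to people for the first time. The Précis says that the reviews are there to make sure the data support going to higher doses.

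The plan treats three subjects at Day 14 as the least it wants to see before escalating. Counting by dose alone does not secure that minimum for the combination. Visit 03 is the first scheduled clinic visit after dosing and the first with CBC and ALT (Appendix III). Section 8.5.1 reports that the related laboratory events in the first trial of the similar chikungunya VLP vaccine were ALT increases and neutropenia, which are what these tests detect.

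**Working it through.** **Nearest stated figure.** The plan gives no operating characteristic for the escalation rule. Section 6.3.1 gives an exact 95% upper bound of 0.522 for no SAE in five subjects, and 1 − 0.025^(1/5) = 0.522 reproduces it. The same formula gives 0.708 for 0/3, 0.842 for 0/2 and 0.975 for 0/1. Three subjects are therefore not precise evidence; three is simply the plan's own minimum.

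**Inputs from the plan.** Five subjects per group, so ten per dose (6.3); 1:1 allocation (6.5); trigger when the third subject at the dose reaches Day 14 (4.3); accrual at the dose complete before the next opens (4.3, 6.5).

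**Assumptions.** Block size, accrual pace and review time are not stated, so ranges are shown. Accrual is even, nobody drops out, and Visit 03 falls exactly on Day 14.

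**Timing.** With one subject every d days and a review lasting r days, the next dose opens at T = max(9d, 2d + 14 + r). The number n with Day 14 data is the number dosed by T − 14.

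**Alum recipients among the n.** With one block of 10, P(k alum) = C(5,k)·C(5,n−k)/C(10,n). Then P(fewer than 3) is:
- n = 3: 110/120 = 0.917
- n = 4: 155/210 = 0.738
- n = 5: 126/252 = 0.500
- n = 6: 55/210 = 0.262
- n = 7: 10/120 = 0.083
- n = 8: 0

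| d (days) | r (days) | n | Fewer than 3 alum | No alum |
|---|---|---|---|---|
| 1 | 0 | 3 | 91.7% | 8.3% |
| 1 | 1 | 4 | 73.8% | 2.4% |
| 1 | 2 | 5 | 50.0% | 0.4% |
| 1 | 3 | 6 | 26.2% | 0% |
| 1 | 5 | 8 | 0% | 0% |
| 2 | 0 | 3 | 91.7% | 8.3% |
| 3 | 0 to 7 | 5 | 50.0% | 0.4% |
| 4 | 0 to 7 | 6 | 26.2% | 0% |
| 5 | 0 to 7 | 7 | 8.3% | 0% |
| 7 | 0 to 7 | 8 | 0% | 0% |

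At d = 3.5, n is already 6, and with five per group six subjects must include an alum recipient.

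**Other block sizes.** The first three subjects always have Day 14 data, so the no-alum case can never be more likely than all three being unadjuvanted. That is 0% with blocks of 2 or a leading block of 4, 1/20 = 5.0% with a leading block of 6, 8.3% with one block of 10 and 0.5³ = 12.5% with simple randomisation. Small blocks do not remove the shortfall below three: with blocks of 2 it is 100% at n = 3 or 4, 50% at n = 5 and 0% at n = 6.

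**What the alum recipients do have.** Subjects dosed by T − 7 have finished the 7-day diary. At d = 1, r = 0, T is day 16 and the tenth subject was dosed on day 9, so all five alum recipients have. At d = 3 with r up to 7, those dosed by day 20 number seven, so at least two alum recipients have. The lowest count is six of ten (for example d = 2, r = 0), so at least one always has.

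**Delay from a per-group rule.** Both groups reach three at the 6th, 7th or 8th subject (k), in 120, 90 and 42 of the 252 orders. The extra wait is max(9d, (k−1)d + 14 + r) − T.
- d = 1: 3, 4 or 5 days; mean (120·3 + 90·4 + 42·5)/252 = 3.7, maximum 5.
- d = 3: maximum 35 − 27 = 8 days at r = 0, and 42 − 27 = 15 days at r = 7.
- d = 7: 0 days at r = 0; maximum 70 − 63 = 7 days at r = 7.

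**The case against.** The strongest reply is that only the VLP dose escalates. Alum stays at 500 mcg, so pooling by VLP dose is a coherent design, and three per formulation is a stricter standard than the plan set itself. The PSRT looks at all available data and must find no significant concern. It meets weekly, the site investigator reviews safety data daily, the pause rules apply with or without adjuvant, and more subjects can be requested first. Most of this stands and limits the risk. But none of it sets a number, and the escalated product in Groups 4 and 6 is the combination.

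Three stronger readings are tempting but not supported.
- A reader might infer that the next alum group could open with no alum safety data. Every subject has a 30-minute observation and a Day 2 call, and with even accrual at least one alum recipient has finished the diary. The gap is at Day 14.
- A reader might take the trigger to count unadjuvanted subjects only, because it echoes the Group 1 label. Section 4.3 limits the pace for the first three subjects at each dose and assesses the dose as a whole, so the dose-level reading is clearly better.
- A reader might take 91.7% as the expected risk. It needs subjects dosed every day or two and an almost immediate review; with only three subjects at Day 14, anything but three alum recipients counts as a shortfall.

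It may also be said that the point comes too late. Letter of Amendment #3 speaks of subjects enrolled in Groups 3-6, which suggests that both reviews may have been held. That affects what can still be done, not whether the rule has the gap.

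**Conclusion.** The point holds as a gap in the escalation rule, with a cheap remedy. Followed exactly, section 4.3 can open the next alum group with fewer than 3 alum recipients at Day 14. Under one block of 10, even accrual, no dropouts and a review of at most 7 days, the chance per escalation runs from 50% at one subject every 3 days to 0% at weekly accrual. It exceeds 50% only with faster accrual and a short review. Having no alum recipient at Day 14 is remote: at most 12.5% under the worst timing and simple randomisation, and 0% at one subject every 3.5 days or slower with five per group. Bunched accrual would raise these figures, because the one-per-day limit covers only the first three subjects at a dose; slow, even accrual removes the problem. What may be missing is the Day 14 clinic visit with the first post-dose CBC and ALT in some alum recipients. The unadjuvanted group likewise has no minimum of its own.

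**What to change.** Amend both triggers in section 4.3, and align section 6.5, so that each review is held, and both next-dose groups open together, only when at least 3 subjects in each of the two groups at the current dose have Day 14 (Visit 03) safety data reviewed by the PSRT. Make the replacement sentence say that the three are required in each group.

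Do not hold back the alum group alone. That would break the concurrent 1:1 randomisation within each dose.

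The cost is a wording amendment plus the delays worked out above: about 4 days on average (maximum 5) per escalation at one subject per day, up to about 15 days at one every 3 days with a 7-day review, and none at weekly accrual with same-day review. Without dropouts, the next dose opens no later than 14 days (17 with the visit window) plus review time after accrual at the dose ends, and no subjects are added. Dropouts could lengthen the wait or require replacements.

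If both reviews have already been held, report how many alum recipients had Day 14 data at each review and when the next dose opened.
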